1.2 Schema

We will undertake a single arm feasibility study with n=20 patients with treatment naïve biopsy proven ILC who have either: a) clinical or imaging suspicion of metastatic disease; b) biopsy proven metastatic disease but in whom there is suspicion of an even greater tumor burden that could change therapy approach. All patients will be recruited from the Winship Glenn Family Breast Cancer Program at any Emory facility and they will have already undergone best standard of care conventional imaging (CT or MR and possibly bone scan depending on clinical presentation). **Standard of care conventional imaging typically does not include FDG PET, since FDG PET is not recommended for lobular cancer due to low sensitivity.** We will then complete both fluciclovine PET and Ga PSMA PET scans on the same patient on separate days separated by at least 10 half-lives to allow for radioactive decay. There is no need for randomization since each patient will undergo both imaging techniques, and the results will be interpreted blindly. Thus, radiopharmacy scheduling will dictate the order of the radiotracers to ensure the patient will undergo both imaging modalities in the shortest time frame. Sometimes this will mean PSMA is completed first, followed by fluciclovine, and other times the opposite. After interpretation of both studies, careful correlation to already obtained conventional imaging will then be done to determine if a previously unsuspected anatomic correlate can be identified which would impact therapy. One or two metastases (depending on scan findings) will then undergo biopsy in the safest manner possible as standard of care (if not already done) to determine the verified detection rate of metastatic disease. Uncommonly, definitive imaging such as MR for skeletal or liver lesions may be accepted in lieu of biopsy, if biopsy is not feasible. We will then compare verified detection rate of each PET study to conventional imaging and to each other. In addition, we will collect peripheral blood for ctDNA in all patients and determine if ctDNA correlates with presence or absence of metastases and tumor burden as identified by conventional imaging, fluciclovine and/or PSMA PET. Study Specific Experimental Procedures will only consist of both PET studies and ctDNA analysis. All other procedures will be conducted per standard of care. See Figure 1.

Figure 1: Trial Schema, Flow diagram

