
Preference for biopsy will be given to discordant lesions. Uncommonly, in some lesions not deemed safe to biopsy, characteristic appearance on correlative imaging will be accepted as truth (e.g., MRI for certain skeletal or liver lesions). In select cases, a second biopsy of a discordant distant lesion may be required. For example, if there are 2 potentially impactful lesions which are fluciclovine positive/PSMA negative and fluciclovine negative/PSMA positive, respectively. Note that before biopsy is considered, careful scrutiny of the already obtained CT or MR will be undertaken to determine if an unsuspected anatomic correlate can be identified. This will then prompt a discussion between the patient and the referring clinician co-investigator on the benefits versus risks to definitively determine if a metastasis is present which could affect therapy. Biopsy may be undertaken in the least invasive manner as standard of care as clinically indicated, reimbursed by third party payers. Uptake parameters will be correlated with all proven primary, locoregional, and distant lesions. Verified detection rates for metastasis will be calculated for each modality.

In addition, we will collect 20 ml peripheral blood for ctDNA analysis in all patients at visit 1 (or possibly 2) to be initially processed and stored by [name] lab for off-site specialty analysis. Plasma levels of ctDNA will be measured using a targeted 28 gene panel to detect point mutations including mutations in PIK3CA, ESR1, HER2, and AKT1, genes associated with hormone therapy resistance and ILC [38, 39]. We will examine ctDNA results for association with presence or absence of locoregional metastasis on imaging as confirmed with histology, presence or absence of distant metastasis on imaging as confirmed with histology, correlation of presence or absence and absolute ctDNA with PET uptake.

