4.2 Scientific Rationale for Study Design

Our preliminary data support a key scientific premise that metabolic imaging with amino acid PET has shown promise in the detection of ILC. There is also emerging data that tumor neovasculature imaging with PSMA PET may improve detection of ILC. **We hypothesize that metabolic imaging with amino acid transporter PET will improve staging of ILC, particularly for distant metastases, compared to best standard of care conventional imaging (usually CT or MR and possible bone scan), and which typically does not include FDG PET due to low sensitivity. We also hypothesize that receptor directed PSMA imaging of tumor associated neovasculature in ILC will reveal unique information to complement metabolic interrogation with fluciclovine PET. Improved staging will facilitate more appropriate management decisions.**

To test these hypotheses with the highest scientific rigor, we propose a feasibility trial with fluciclovine and Ga-PSMA PET strategies centered on detection of metastasis in patients with advanced ILC using histology as the gold standard. As an exploratory aim, we will also correlate the occurrence of circulating tumor DNA (ctDNA) mutations including PIK3CA, ESR1, HER2, and AKT1 with presence of metastasis and tumor burden. We will explore if a multiparametric strategy with ctDNA and imaging will help define which patients should undergo molecular imaging and also identify those who may forego biopsy if distant lesions are detected on imaging. We expect this pilot trial will generate sufficient preliminary data to determine feasibility for a definitive NIH sponsored trial developing more accurate staging techniques to help modify current practice for imaging of ILC.

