8.1 Schedule of Procedures

See above schedule of activities in Section 1.3 for **study specific experimental procedures**.

Standard of Care Procedures

1) Conventional imaging is broadly defined as mammography, ultrasound, bone scan, FDG PET, CT and/or MR: Any or all of these imaging studies may have been performed as standard of care at enrollment. These are not under control of study design. Conventional imaging and reports within 6 months of enrollment (ideally 2 months) will be reviewed to correlate to PET imaging. No additional interpretation will take place. Imaging reports for these studies will be utilized for comparative analysis.

2) Biopsy: After the PET studies, patients with abnormal findings on the PET scans will have the most distant and accessible lesion identified so that the patient may undergo biopsy in the safest manner possible (if not already done) as clinically indicated. Preference for biopsy will be given to discordant lesions. In some lesions not deemed safe to biopsy, characteristic appearance on correlative imaging will be accepted as truth (e.g., MRI for certain skeletal or liver lesions). In select cases, a second biopsy of a discordant distant lesion may be required. Note that before biopsy is considered, careful scrutiny of the already obtained CT or MR will be undertaken to determine if an unsuspected anatomic correlate can be identified. This will then prompt a discussion between the patient and the referring clinician co-investigator on the benefits versus risks to definitively determine if a metastasis is present which could affect therapy. Biopsy will be undertaken in the least invasive manner as standard of care, reimbursed by third party payers.

3) Therapy: All subsequent therapy for breast cancer will be standard of care and beyond the scope of this investigation.

9. Measurement of Effect

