ctDNA analysis: Plasma levels of ctDNA will be measured using targeted assays to detect point mutations including mutations in PIK3CA, ESR1, HER2, and AKT1, genes associated with hormone therapy resistance and ILC [12, 38, 39, 43]. Because ILC are predominantly hormone receptor positive, hormone resistance is particularly relevant because it predicts for higher rate of distant metastasis. [name], will provide expertise in ctDNA analyses. Deidentified specimens will be shipped to the Circulating Tumor Cell Center at Massachusetts General Hospital for fee for service ctDNA processing.

Correlation of ctDNA results with results of imaging: We will examine ctDNA results for association with presence or absence of locoregional metastasis on imaging as confirmed with histology, presence or absence of distant metastasis on imaging as confirmed with histology, correlation of presence or absence and absolute ctDNA with PET uptake as determined by the following indices: SUVmax, SUVmean, SUVpeak, Total Lesson Activity for the index primary, locoregional and distant metastatic lesion if any, and correlation to summed indices as a reflection of total metabolic tumor burden. ctDNA will also be correlated with CI.

10. Statistical considerations

Specific Aims 1 and 2

Analysis plan: The objectives of Aims 1 and 2 are to compare verified detection rates between fluciclovine and PSMA PET versus conventional imaging, as confirmed with histology (Aim 1), and determine concordance and discordance of ILC detection with PSMA versus fluciclovine PET, as confirmed with histology (Aim 2). Paired detection rates will be assessed using McNemar's test.

Detection rates will be reported for each method, and 95% confidence intervals will be estimated using the Clopper-Pearson approach. Rates of concordant/discordant observations will be reported. The Likert rating-scale data also allows for determination of sensitivity, specificity, PPV, NPV and Receiver Operating Characteristic (ROC) Area Under the Curve (AUC) values to compare.

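### In Aim 1 the same MR can be both conventional-imaging comparator and accepted truth, so for some unbiopsied lesions conventional imaging would be verified by its own call

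*Combined protocol and SAP*

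**What the plan says.** **Truth.** Section 10 states the Aim 1 objective as to "compare verified detection rates between fluciclovine and PSMA PET versus conventional imaging, as confirmed with histology (Aim 1". Sections 1.1 and 3.1 word Aims 1 and 2 the same way, and Section 4.2 describes the trial as "using histology as the gold standard".

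**Comparator.** Section 1.2 says of the patients that "they will have already undergone best standard of care conventional imaging (CT or MR and possibly bone scan depending on clinical presentation". Section 8.1 is wider: "Conventional imaging is broadly defined as mammography, ultrasound, bone scan, FDG PET, CT and/or MR". The comparator is scored from what was already reported, with no new reading: "Imaging reports for these studies will be utilized for comparative analysis".

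**Exception to histology.** Section 4.1: "characteristic appearance on correlative imaging will be accepted as truth (e.g., MRI for certain skeletal or liver lesions". Section 1.2, repeated in footnote c of Section 1.3: "definitive imaging such as MR for skeletal or liver lesions may be accepted in lieu of biopsy, if biopsy is not feasible". Section 4.1 limits its sentence with "Uncommonly, in some lesions not deemed safe to biopsy"; the parallel sentence in Section 8.1 drops the adverb. No section gives a number or a cap.

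**Which MR.** Section 2.3, in the MR item under risks of non-study procedures, describes an MR done after a lesion is judged unsuitable for biopsy, so the truth MR can be a later scan. No section says that it must be.

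**Analysis.** Section 10 gives detection rates with Clopper-Pearson intervals and McNemar's test for paired rates. It has no rule for lesions verified by imaging and no histology-only analysis.

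**The concern.** A reference standard should not contain the test that it judges. Here MR can sit on both sides of the Aim 1 comparison. If the MR already in the conventional work-up called a lesion metastatic, biopsy was not feasible, and that MR is accepted as truth, then conventional imaging is scored as a verified detection because it said so itself. A false-positive call by that MR could not be exposed.

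This matters in this disease by the protocol's own account. Section 1.1 lists whole-body MR among the modalities on which lobular cancer is hard to see, and Section 2.3 gives false-positive conventional imaging as one reason why molecular imaging might help.

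At stake is the PET-versus-conventional contrast in a pilot whose stated purpose (Section 10) is to estimate an effect size for a larger trial.

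**Working it through.** **1. The plan's own figures.** The point rests on no stated number, but Section 10's planning figures supply a scale. For difference δ and discordant proportion ψ, the power of the exact McNemar test with N patients is

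Σₘ Bin(m; N, ψ) × P(X ≥ cₘ), where X ~ Bin(m, (ψ+δ)/(2ψ)) and cₘ is the smallest x with P(Bin(m, ½) ≥ x) ≤ 0.05.

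With δ = 0.20 and ψ = 0.40, (ψ+δ)/(2ψ) = 0.60/0.80 = 0.75. The smallest N with at least 80% power is 67 (power 0.805), as stated. The same one-sided exact rule returns all seven stated sizes: 67, 83, 99, 118, 175, 42 and 63. Section 10 does not state sidedness; that is a separate matter, and the one-sided rule is used here only because it reproduces the plan.

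**2. Where the overlap bites.** Take a lesion not biopsied and verified by MR:

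| Comparator report | Truth MR | Score for conventional imaging | Self-verified? |
|---|---|---|---|
| MR called the lesion | same MR | detected, necessarily | yes |
| MR called the lesion | separate later MR | detected | not by the same image; same modality, so errors may be correlated |
| MR did not report the lesion | separate later MR | missed | no |
| no MR in the work-up | later MR | by the report | no |

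Only the first row is incorporation in the strict sense. If PET is also positive, the row adds a concordant patient and leaves McNemar's test unchanged. If PET is negative, it adds a conventional-only pair.

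**3. Scale of one patient (assumed counts).** The documents do not say how many lesions would be verified by MR. Assume one pair per patient, all 20 patients in the denominator, and a true result of 6 PET-only and 2 conventional-only pairs. Then δ = (6−2)/20 = 20% and ψ = 8/20 = 40%, Section 10's lead case.

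- One patient with a PET-negative lesion accepted on the comparator MR gives 6 and 3 pairs: δ = 3/20 = 15%, ψ = 9/20 = 45%. The same method gives N = 132 in place of 67.
- One PET-only patient lost because MR appearance is taken as truth against the PET finding gives 5 and 2 pairs: δ = 3/20 = 15%, ψ = 7/20 = 35%, N = 103.
- The two-sided exact McNemar p-value moves from 2×(1+8+28)/256 = 0.289 to 2×(1+9+36+84)/512 = 0.508 in the first case, and to 2×(1+7+21)/128 = 0.453 in the second.

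Each step is 1/20 = 5 points. With the 10% dropout expected in Section 5 (18 patients) it would be 1/18 = 5.6 points. None of these p-values is near significance, so a shift of this kind lies well inside sampling error at n = 20. It differs from sampling error in being systematic and avoidable.

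**4. Direction.** Both cases in step 3 favour conventional imaging. A later MR prompted by a PET finding could favour PET if its reader knows the PET result. The documents do not say who reads it or under what blinding, so the net direction cannot be signed.

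**The case against.** The case on the other side is substantial, and most of it stands as a limit on the point.

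- **The exception is disclosed and narrow.** It applies when biopsy is unsafe or not feasible, and most sections call it uncommon. The missing adverb in Section 8.1 is minor. The study is an unpowered pilot.
- **The truth MR may be a later scan.** Section 2.3 describes that sequence, while the comparator is scored from earlier reports. Aim 1 also directs attention to lesions that the earlier imaging had not raised. For those, a later MR that confirms the lesion scores conventional imaging as a miss, so a reader who infers that conventional imaging is right by construction throughout goes too far.
- **Knowledge of PET is inference.** It is plausible that a PET-prompted MR is read with the PET result to hand, but no section says so.
- **Aim 2 is not exposed in the same way.** MR is neither test in PET versus PET, so only the histology wording needs attention there. The primary endpoint in Section 3.2 is likewise the verified detection rate on the two PETs.
- **A shrinking difference in rates is not evidence of the bias.** A reader might add three MR-verified patients, positive on both PET and conventional imaging, to an assumed 8/9 against 5/9. That gives 11/12 against 8/12, and the gap falls from 33 to 25 points. The excess is 3 patients both times, the discordant pairs are the same, and McNemar's result is the same. Three histology-proven concordant patients would have the same effect.
- **Histology alone is not a clean standard.** Sections 4.1 and 8.1 prefer discordant lesions for biopsy and look for accessible ones, so a histology-only set has partial-verification bias of its own.

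What none of this removes: the aims state one reference standard and the procedures use another, and no rule stops the comparator MR from serving as truth.

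**Conclusion.** The inconsistency is in the text, and following the plan as written can credit conventional imaging by its own call. The effect is confined to lesions verified by MR in patients whose conventional imaging included MR, and in its strict form to lesions where both roles fall to one scan. Its size and net direction are unknown, because the documents give neither the number of MR-verified lesions nor the conditions under which the truth MR is read. The 5 points per patient, and the move in follow-on sample size from 67 to 103 or 132, are scale only. They rest on assumed pair counts, 20 evaluable patients and one pair per patient.

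A reader might infer that the Aim 1 comparison cannot be interpreted at all. The documents do not support that. It can be interpreted once results are broken down by how each lesion was verified, and the plan does not yet provide for this.

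**What to change.** 1. In Section 10, reconcile the histology wording of Aims 1 and 2 with the imaging exception in Sections 1.2, 1.3, 4.1 and 8.1, so that one reference standard is described throughout.
2. Record for each lesion whether it was verified by histology or by imaging and, if by imaging, whether that scan is also the patient's comparator study.
3. Report the Aim 1 detection rates, Clopper-Pearson intervals and McNemar result for histology-verified lesions beside the same results under the composite reference.
4. In the composite, do not count a lesion as verified for the conventional-imaging comparison when its only source of truth is the MR that serves as the comparator. Lesions confirmed by a separate later MR stay in and are scored against the original report, so genuine PET-only detections are kept.

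Set these rules before lesions are adjudicated, so that results cannot guide the choice.

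**Cost.** Some wording, one or two extra data fields and one extra tabulation, with no added procedure. The histology-verified set will be smaller, with wider intervals, and will over-represent discordant and accessible lesions. It should therefore be shown alongside the composite and not presented as unbiased.

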4.2 Scientific Rationale for Study Design

Our preliminary data support a key scientific premise that metabolic imaging with amino acid PET has shown promise in the detection of ILC. There is also emerging data that tumor neovasculature imaging with PSMA PET may improve detection of ILC. **We hypothesize that metabolic imaging with amino acid transporter PET will improve staging of ILC, particularly for distant metastases, compared to best standard of care conventional imaging (usually CT or MR and possible bone scan), and which typically does not include FDG PET due to low sensitivity. We also hypothesize that receptor directed PSMA imaging of tumor associated neovasculature in ILC will reveal unique information to complement metabolic interrogation with fluciclovine PET. Improved staging will facilitate more appropriate management decisions.**

To test these hypotheses with the highest scientific rigor, we propose a feasibility trial with fluciclovine and Ga-PSMA PET strategies centered on detection of metastasis in patients with advanced ILC using histology as the gold standard. As an exploratory aim, we will also correlate the occurrence of circulating tumor DNA (ctDNA) mutations including PIK3CA, ESR1, HER2, and AKT1 with presence of metastasis and tumor burden. We will explore if a multiparametric strategy with ctDNA and imaging will help define which patients should undergo molecular imaging and also identify those who may forego biopsy if distant lesions are detected on imaging. We expect this pilot trial will generate sufficient preliminary data to determine feasibility for a definitive NIH sponsored trial developing more accurate staging techniques to help modify current practice for imaging of ILC.

4.3 Justification for Dose

The doses administered for each radiotracer: 10 mCi fluciclovine (¹⁸F) and 5 mCi for Ga PSMA are based upon well established guidelines referenced below.

4.4 End of Study Definition

The study will be closed to accrual once all 20 patients have been recruited and scanned with PET. End of analysis will occur once sufficient followup data has been collected for each patient to determine study endpoints. Study will be formally closed once all manuscripts have been published. Though it is likely most relevant standard of care followup will be acquired within 1 year, patients will be consented for 5 year followup through the medical record in the case of future required analysis. There will be no other study specific visits after the second PET scan (visit 2), though the patient will be called by the study nurse at 5-10 business days to ensure no delayed AEs occurred.

5. Study Population

Approximately 1400 breast cancer patients are seen yearly at Winship, with approximately 20% of lobular histology (280). Of these, approximately 100-150 are advanced. Thus at a conservative recruitment rate of 10% (10-15 patients/year), successful accrual is highly feasible. Lobular cancer tends to present at a higher stage. Based on historical averages, we expect that 31% of patients will present with Stage 3 and 37% of patients with Stage 4 disease. We expect approximately 10% dropout either before completion of both PET scans or after PET scanning and before biopsy.

5.1 Inclusion Criteria

- (Y) 1. Treatment naïve biopsy proven ILC Patients with ILC
- (Y) 2. Either: a) clinical or imaging suspicion of metastatic disease; or b) proven metastatic disease but in whom there is suspicion of an even greater tumor burden that could change therapy approach.
- (Y) 3. Ability and willingness to undergo biopsy if needed per standard of care for possible metastasis which could change therapy approach.
- (Y) 4. Age over 18

Non-English-speaking patients may be considered for enrollment in this trial. Subjects with Limited English Proficiency LEP may be enrolled and study team members will use Emory IRB approved short forms to conduct the consent process.

5.2 Exclusion Criteria

- (N) 1. Pregnancy. Qualitative or quantitative serum or urine pregnancy test will be done in women of childbearing potential within 24 hours before PET¹.

¹ A female of childbearing potential (FCBP) is a sexually mature woman who: 1) has not undergone a hysterectomy or bilateral oophorectomy; or 2) has not been naturally postmenopausal for at least 12 consecutive months (if age > 55 years); if the female subject is < 55 years and she has been naturally postmenopausal for > 1 year her reproductive status has to be verified by additional lab tests (< 20 estradiol OR estradiol < 40 with FSH > 40 in women not on estrogen replacement therapy).

6. Registration Procedures

Informed consent is required prior to participation in the study. Patients will sign the written informed consent, if possible, at the time of enrollment. In instances where this is not possible, verbal informed consent will be first obtained in order to instruct the patient to fast in preparation for the fluciclovine PET scan (not required for PSMA). However final written informed consent will be obtained before the PET scan. Participants will also be assigned an identification number for screening purposes; data collected during the screening process will also be recorded using that number. Patients will then be registered in OnCore through usual Winship and department of Radiology and Imaging Sciences guidelines. No randomization will be performed. Blinding will only take place for initial study interpretation before consensus interpretation by Nuclear Medicine imagers.

7. Study Intervention

Radiotracer production: Blue Earth Diagnostics, Ltd manufacturers of fluciclovine has pledged support with gratis radiotracer unit doses supplied from PETNET Solutions.

Telix Pharmaceuticals (US) Inc, manufacturer of Ga-PSMA, has pledged support with gratis radiotracer kits which will be compounded by the Emory CSI radiopharmacy.

Fluciclovine

PETNET Solutions, located on the Emory campus, produces commercial doses of fluciclovine which is FDA-approved for the detection of recurrent prostate cancer. Unit doses of this material will be provided for the study. The IRB has decided that a formal IND exemption is not required.

The following is provided as justification for IND exemption: This is an early phase study in which 20 female patients will undergo fluciclovine and PSMA PET on separate days. We have already studied 12 female patients with fluciclovine in the past for breast cancer under an Emory IRB approved protocol without safety concerns. At the time, the fluciclovine radiotracer was manufactured at the Emory CSI radiopharmacy under [name] existing IND 072437. Yet, we will now be administering FDA approved commercial doses supplied by the commercial radiopharmacy PETNET to which our IND would not be applicable. Thus, this is off-label research of an FDA approved product for recurrent prostate cancer. The patient will undergo pregnancy testing within 24 hours before PET as appropriate per Winship and Radiology regulations. Note also that 27 women had also been studied for this indication at Sloan Kettering in the past without complication. Three female normal volunteers and a number of other female patients with other cancers have been studied with fluciclovine under our IND without complication and this data had been used to obtain FDA approval in terms of safety. Thus, we believe an IND exemption is in order since: 1) The investigation is not intended to be reported to FDA as a well-controlled study in support of a new indication for use nor intended to be used to support any other significant change in the labeling for the drug; 2) The drug that is undergoing investigation is lawfully marketed as a prescription drug product, and the investigation is not intended to support a significant change in the advertising for the product; 3) The investigation is conducted in compliance with the requirements concerning the promotion and sale of drugs; 4) The investigation is conducted in compliance with the requirements for IRB review and informed consent; 5) The investigation does not intend to invoke 21 CFR 50.24, a waiver of informed consent in an emergency room setting.

PSMA

⁶⁸Ga-PSMA will be produced under [name] IND #143137 via a lyophilized kit produced by Telix Pharmaceuticals. Briefly, ⁶⁸Ga will be eluted from our Eckerd and Ziegler 50 mCi Pharmaceutical Grade ⁶⁸Ge/⁶⁸Ga Generator (or equivalent) located at our in-house radiopharmacy and combined in a vial with the premixed lyophilized product including peptide. Our existing PSMA IND #143137 has been amended with the study protocol.

